12.2. Secondary Effectiveness and OCS Donor Liver Assessment Endpoints

The secondary effectiveness and OCS donor liver assessment endpoints for this trial are as follows:

- OCS donor liver assessment during perfusion, defined as, among donor livers preserved using OCS for the entire preservation period, the proportion of livers on which measurements of all of the following during perfusion will be available on OCS device before transplant
 - Lactate level (every two hours +20 mins. of time window)
 - Average bile production rate (based on total bile production volume and duration of OCS perfusion)
 - Hepatic Artery Pressure (continuously averaged every 30 minutes)
 - Portal Vein Pressure (continuously averaged every 30 minutes)
- Patient survival at Day 30 post-transplantation
- Patient survival at time of initial hospital discharge post-transplantation

The null and alternative hypotheses for the OCS donor liver assessment during perfusion endpoint are:

$$\begin{aligned} H_0: \pi_3 &\leq 0.85 \text{ and} \\ H_1: \pi_3 &> 0.85, \end{aligned}$$

respectively, where π_3 is the true proportion of livers, among donor livers preserved using OCS for the entire preservation period, on which measurements of lactate level, average bile production rate, Hepatic Artery Pressure and Portal Vein Pressure during perfusion were available on OCS device before transplant.

This secondary endpoint of OCS donor liver assessment during organ perfusion will be analyzed by calculating the sample proportion of donor livers placed on OCS meeting the criteria for this endpoint, as well as an exact (Clopper-Pearson) 95% one-sided lower confidence bound for the corresponding population proportion. A lower confidence bound greater than 0.85 will result in rejection of the null hypothesis in favor of the alternative hypothesis and demonstration that the true proportion is greater than 0.85 for the OCS donor liver assessment endpoint. If information for any of the four measurements is missing, the donor liver will be classified as not meeting the OCS donor liver assessment criteria. This secondary endpoint will be analyzed using the Donor Liver Population but limited to livers preserved with OCS for the entire preservation period.

Each secondary effectiveness endpoint will be summarized by treatment group using the count and percentage and the exact (Clopper-Pearson) 95% confidence interval for the true percentage based on the binomial distribution. The secondary effectiveness endpoints will be analyzed using the Per Protocol and mITT Populations, with the Per Protocol analysis being considered the primary analysis.

The statistical hypotheses for the first secondary effectiveness endpoint, patient survival at Day 30 post-transplantation, are as follows:

$$\begin{aligned} H_{20}: \pi_{2,\text{OCS}} &\leq \pi_{2,\text{CONTROL}} - \delta \text{ and} \\ H_{21}: \pi_{2,\text{OCS}} &> \pi_{2,\text{CONTROL}} - \delta, \end{aligned}$$

where $\pi_{2,\text{OCS}}$ and $\pi_{2,\text{CONTROL}}$ are the true proportions of subjects surviving to Day 30 post-transplantation for the OCS and standard of care treatments, respectively, and δ is the non-inferiority margin, which is here taken to be 0.075. This endpoint will be analyzed by calculating the 95% one-sided upper confidence bound based on the Farrington and Manning score statistic for the difference between the two population proportions ($\pi_{2,\text{CONTROL}} - \pi_{2,\text{OCS}}$). An upper confidence bound less than $\delta = 0.075$ will result in rejection of the null hypothesis (H_{20}) in favor of the alternative hypothesis (H_{21}) and demonstration of non-inferiority of OCS to Control. In the event non-inferiority is demonstrated, Fisher's exact test (two-sided) will be used to test for superiority.

The second secondary effectiveness endpoint, patient survival at initial hospital discharge post liver transplantation, will be analyzed in a manner analogous to the first secondary effectiveness endpoint with the same non-inferiority margin of 0.075.

Because fixed sequence testing will be used for the secondary endpoints, no adjustment for the multiplicity of these endpoints needs to be made. The endpoints will be tested in the order listed above. The test for non-inferiority for the first secondary effectiveness endpoint will be performed only if the null hypothesis has been rejected for the OCS donor liver assessment endpoint. The test for non-inferiority for the second secondary effectiveness endpoint will be performed only if the null hypothesis has been rejected in favor of the alternative hypothesis of non-inferiority of the OCS treatment to the Control treatment for the first secondary effectiveness endpoint. Similarly, the test for superiority for the second secondary effectiveness endpoint will be performed only if the null hypothesis of equality has been rejected in favor of superiority of the OCS treatment to the Control treatment for the first secondary effectiveness

endpoint (and non-inferiority has been demonstrated for the given secondary effectiveness endpoint). Due to statistical power limitations, it is not expected that non-inferiority will be demonstrated for patient survival at day 30 or at initial hospital discharge.

Multiple imputation methods, as described in Section 5.3, will be used for data imputation for patients with missing values for the patient survival secondary endpoints.

Assuming the Per Protocol Population analysis of a patient survival secondary endpoint with imputation of missing data results in rejection of the null hypothesis in favor of non-inferiority, a tipping point sensitivity analysis based on the Per Protocol Population as described in Section 5.4 will be used to assess the effect of missing data for the relevant patient survival secondary endpoint. A tipping point sensitivity analysis will also be performed using the mITT population if the analysis of a patient survival secondary efficacy endpoint with imputation of missing data based on the mITT Population results in rejection of the null hypothesis in favor of non-inferiority.

Subgroup analyses of the secondary effectiveness endpoints will be performed for the subgroups indicated in Section 5.9. No data imputation or statistical tests will be performed for these subgroup analyses. In addition, analyses of each secondary effectiveness endpoint by donor inclusion criteria will be performed using observed data. In these analyses, the endpoint will be reported for the proportion of subjects meeting each individual donor inclusion criteria, a single donor exclusion criteria, multiple donor exclusion criteria, and at least one donor exclusion criteria. No data imputation or statistical tests will be performed for these analyses based on donor inclusion criteria. The subgroup analyses and the donor inclusion analyses will be performed for both the Per Protocol and mITT populations.

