
Effectiveness Analysis
	
The primary effectiveness endpoint for this study is Early Liver Allograft Dysfunction (EAD), defined as presentation of one or more of the following criteria:
 
 • AST level >2000 IU/ml within the first 7 postoperative days; • Bilirubin ≥ 10 mg/dl on postoperative day 7; • INR ≥ 1.6 on postoperative day 7; or • Primary non-functioning graft within the first 7 days 
The primary hypothesis for this study is that the OCS treatment is non-inferior to the standard of care treatment with respect to this endpoint. The non-inferiority margin δ is taken to be 0.075. If non-inferiority is demonstrated using a significance level of 0.05, a two-sided test of superiority will be performed.
 
The primary effectiveness endpoint will be analyzed by calculating, for each treatment group, the sample proportion of subjects meeting the primary effectiveness endpoint, as well as an exact (Clopper-Pearson) 95% confidence interval for the corresponding population proportion. The 95% upper bound of the exact unconditional one-sided confidence interval based on Farrington and Manning score statistic will be calculated for the difference between the two population proportions (OCS – Control). An upper confidence limit less than $\delta = 0.075$ will result in rejection of the null hypothesis in favor of the alternative hypothesis and the demonstration of non-inferiority of OCS to Control for the primary effectiveness endpoint. In the event non-inferiority is demonstrated, Fisher's exact test (two-sided) will be used to test for superiority.
 
This endpoint will be analyzed using the Per Protocol and mITT Populations. The Per Protocol analysis will be considered the primary analysis. Multiple imputation methods will be used for data imputation for any patients with missing values for this endpoint.
 
The secondary effectiveness and OCS donor liver assessment endpoints for this trial, listed in the order in which they will be tested using the fixed sequence testing procedure, are as follows:
 
 • OCS Measurements during organ perfusion • Patient survival at day-30 post-transplantation • Patient survival at initial hospital discharge post liver transplantation 
The hypothesis for the endpoint of OCS donor liver assessment during perfusion is that, among donor livers preserved using OCS for the entire preservation period, the proportion of livers on which measurements of lactate level, average bile production rate, Hepatic Artery and Portal Vein Pressure during perfusion are available on OCS device before transplant is at least 85%. This endpoint will be analyzed by calculating the sample proportion of donor livers meeting the endpoint, as well as an exact 95% one-sided lower confidence bound for the corresponding population proportion. A lower confidence bound greater than 0.85 will result in the demonstration that the true proportion is greater than 0.85 for the OCS donor liver

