3.4. Determination of Sample Size

The sample size for this trial was determined based on the primary effectiveness endpoint, Early Liver Allograft Dysfunction (EAD) in the first 7 days post-transplantation. The sample size calculation assumed a one-sided, normal approximation test for non-inferiority, an alpha level of 0.05, a non-inferiority margin of 0.075, a 1:1 allocation, true proportions for the primary effectiveness endpoint of 0.2 for the OCS treatment and 0.25 for the Control treatment, and power of 80%. Based on these specifications, the required sample size was determined to be 144 transplanted recipients per treatment group, or 288 total transplanted subjects. To ensure an

adequate number of subjects in the Per Protocol Population, the sample size was increased to a total of 300 transplanted subjects. Subjects will be enrolled until there are either 290 subjects in the Per Protocol Population or a total of 300 transplanted subjects, whichever comes first.

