5.8. Multiple Comparisons / Multiplicity

No adjustments for multiple comparisons/multiplicity will be made. Because fixed sequence testing will be used for the secondary effectiveness endpoints, no adjustment for the multiplicity of these endpoints needs to be made. The fixed sequence testing is shown below.

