12. ANALYSIS OF EFFECTIVENESS ENDPOINTS

12.1. Primary Effectiveness Endpoint

The primary effectiveness endpoint for this study is Early Liver Allograft Dysfunction (EAD), defined as presentation of one or more of the following criteria:

- AST level > 2000 IU/ml within the first 7 postoperative days
- Bilirubin ≥ 10 mg/dl on postoperative Day 7
- INR ≥ 1.6 on postoperative Day 7
- Primary non-functioning graft within the first 7 days (defined as irreversible graft dysfunction requiring emergency liver re-transplantation or resulting in death, in the absence of immunologic or surgical causes)

The primary hypothesis for this study is that the OCS treatment is non-inferior to the standard of care treatment with respect to this endpoint. The primary statistical hypotheses are as follows:

$$H_{10}: \pi_{1,OCS} \geq \pi_{1,CONTROL} + \delta \text{ and}$$

$$H_{11}: \pi_{1,OCS} < \pi_{1,CONTROL} + \delta,$$

where $\pi_{1,OCS}$ and $\pi_{1,CONTROL}$ are the true proportions of subjects with Early Liver Allograft Dysfunction for the OCS and standard of care treatments, respectively, and δ is the non-inferiority margin, which is here taken to be 0.075.

The primary effectiveness endpoint will be analyzed by calculating, for each treatment group, the sample proportion of subjects meeting the primary effectiveness endpoint, as well as an exact (Clopper-Pearson) 95% confidence interval for the corresponding population percentage. The 95% exact unconditional one-sided upper confidence bound based on the Farrington and Manning score statistic will be calculated for the difference between the two population proportions ($\pi_{1,OCS} - \pi_{1,CONTROL}$). An upper confidence bound less than $\delta = 0.075$ will result in rejection of the null hypothesis (H_{10}) in favor of the alternative hypothesis (H_{11}) and the demonstration of non-inferiority of OCS to control for the primary effectiveness endpoint. In the event non-inferiority is demonstrated, Fisher's exact test (two-sided) will be used to test for superiority.

This endpoint will be analyzed using the Per Protocol and mITT Populations. The Per Protocol analysis will be considered the primary analysis. Analyses will first be performed without any imputation of missing data. If there are any missing data for this endpoint, multiple imputation methods will be used for data imputation for any patients with missing values for this endpoint. The multiple imputation methods are described in Section 5.3.

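### As written, the secondary fixed sequence starts at OCS measurement availability and does not depend on the primary EAD non-inferiority test succeeding

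*SAP*

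**What the plan says.** The primary test is EAD non-inferiority in the Per Protocol Population, with a margin of 0.075 and a one-sided 95% bound (Protocol 9.3.1, SAP 12.1). If it succeeds, Fisher's "exact test (two-sided) will be used to test for superiority" on the same endpoint.

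The secondary endpoints are "listed in the order in which they will be tested using the fixed sequence testing procedure" (Protocol synopsis, Effectiveness Analysis): measurement availability, then day-30 survival, then survival at initial discharge. Protocol 9.3.2 and SAP 12.2 keep this order and spell out the dependencies:

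- Day-30 survival non-inferiority "will be performed only if the null hypothesis has been rejected for the OCS donor liver assessment endpoint".
- Discharge survival non-inferiority requires day-30 non-inferiority.
- Discharge survival superiority requires day-30 superiority, and discharge non-inferiority as well.

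None of the three places makes the availability test, or any later step, depend on EAD non-inferiority. On the analysis set for availability, SAP 12.2 says: "This secondary endpoint will be analyzed using the Donor Liver Population but limited to livers preserved with OCS for the entire preservation period". It gives no number of livers.

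SAP 5.8 says "No adjustments for multiple comparisons/multiplicity will be made", adds that fixed-sequence testing makes adjustment among the secondary endpoints unnecessary, and closes with "The fixed sequence testing is shown below". Nothing follows it in the text available. SAP 5.1 sets 0.05 as the default level for every test.

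Protocol 9.3.2 and SAP 12.2 also say that, for reasons of power, "it is not expected that non-inferiority will be demonstrated for patient survival at day 30 or at initial hospital discharge".

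**The concern.** A fixed sequence protects the error rate only from its own first step onward. Here that step is a device-performance question (are the readings available in more than 85% of livers?), and the primary clinical hypothesis stands outside the chain. The primary and the secondary sequence are therefore two separate routes to a formal claim, each at one-sided 0.05. The chance of at least one false claim across the two is not held at 5%.

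The practical stake is what may be claimed after a failed primary. The plan accepts a 20% chance of that even if its assumptions hold. It does not say that formal secondary testing then stops, so the question would be settled after the result is known.

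The power sentence is a smaller matter. It tells the reader what to expect of the survival tests without giving the survival rates behind that expectation.

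**Working it through.** **Inputs.** From SAP 3.4: one-sided alpha 0.05, margin 0.075, EAD 20% OCS and 25% Control, 80% power, 144 per arm. From SAP 12.2: availability null of 85%, exact one-sided 95% lower bound. From SAP 3.4: "Subjects will be enrolled until there are either 290 subjects in the Per Protocol Population or a total of 300 transplanted subjects". That gives 290/2 = 145 and 300/2 = 150 per arm. Using 145 or 150 as the number of fully OCS-preserved livers is an assumption, because the availability set is not tied to either figure.

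**The plan's own figure.** With the exact unconditional Farrington-Manning test named in the synopsis, 144 per arm gives power 0.810 at 20% against 25%, so the stated size reproduces. The plain normal approximation named in Protocol 9.6 and SAP 3.4 gives 138. The difference does not bear on this point.

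**Size of the availability test.** The lower bound exceeds 0.85 with:

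- at least 131 of 145 livers; P(X ≥ 131 | n = 145, p = 0.85) = 0.0403
- at least 135 of 150 livers; P(X ≥ 135 | n = 150, p = 0.85) = 0.0493

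**At least one false claim on EAD or availability.** Both nulls are at their boundary, the tests are taken as independent, and the primary is at its nominal 0.05:

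- 145 livers: 1 − 0.95 × (1 − 0.0403) = 0.088
- 150 livers: 1 − 0.95 × (1 − 0.0493) = 0.097
- both tests at nominal 0.05: 1 − 0.95² = 0.0975
- without independence, at most 0.05 + 0.05 = 0.10

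If the availability test is opened only after EAD non-inferiority, a false claim in this setting must begin with a false primary claim, so the chance returns to the nominal 0.05.

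**How often the situation arises.** If true availability is 95%, the first secondary step passes with probability 0.994 (145 livers) or 0.996 (150), whatever happens to the primary. Primary power, enumerated with the score statistic against 1.645:

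| True EAD, OCS / Control | Power, 145 / 150 per arm | Primary missed |
|---|---|---|
| 20% / 25% | 0.819 / 0.831 | 18% / 17% (20% by the plan's stated power) |
| 25% / 25% | 0.434 / 0.445 | 57% / 55% |

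At 145 and the planned rates, a missed primary together with a passed availability test has probability of about (1 − 0.819) × 0.994 = 0.18 under independence. The availability claim would be true in that case. The issue there is its formal status after a failed primary.

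**Minor point, survival power.** Day-30 non-inferiority with the SAP's Farrington-Manning test at 145 per arm, all survival rates assumed:

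| Survival, OCS / Control | Power |
|---|---|
| 97.5% / 97.5% | 97% |
| 95% / 95% | 86% |
| 90% / 90% | 67% |
| 94.5% / 97.5% | 55% |

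The only 30-day survival figures in the documents are in the small cited feasibility study of another device (Protocol 1.4.4): 97.5% with cold storage, where the count in the cell is corrupt, and 100% with machine perfusion. Discharge survival was not computed, since it has no fixed time point.

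**The case against.** Several counter-arguments have force.

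- **The display missing from SAP 5.8 may already start with the primary.** This stands as a limit on confidence. Text lost in extraction is not an omission from the plan. The prose in three places still lacks the condition and would need to match such a display.
- **The plan makes no false statement.** This also stands. It says only that no adjustment is needed among the secondary endpoints, and a fixed sequence does justify that within the non-inferiority chain. A reader might infer that the statement is itself the error; the documents do not support that. What is missing is control across the primary and the secondaries together.
- **EAD superiority is outside the sequence.** A reader might infer a further inflation. That test is nested under EAD non-inferiority on the same endpoint and does not inflate error by itself. If the proposed condition is added and superiority stays where it is, the chance of a false EAD superiority or availability claim, with EAD 25% in both arms and availability at its null, is 3.5% (145) or 4.0% (150). It exceeds 5% only at 150 and with EAD near 3% (5.6%), far from the planned rates. No reordering is warranted.
- **The 8.8% to 9.7% needs both nulls to be true.** Correct. It is a worst-case error rate for two tests. It leaves out the safety tests that SAP 13 runs separately at 0.05. The 10% bound takes each test at its nominal level.
- **The EAD figures use the score cut-off, and SAP 12.1 names the exact test.** The exact test gives power 0.814 and 0.823 at 145 and 150, which changes nothing.
- **The power sentence affects no decision.** Agreed, and it is therefore minor. A reader might infer that it is wrong. With an OCS arm 3 points worse, power is only about 55%, so the sentence is unsupported and has not been disproved.

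**Conclusion.** The point holds, with moderate confidence because of the missing display. In the available prose of the synopsis, Protocol 9.3.2 and SAP 12.2, formal secondary testing does not depend on the primary. Error across EAD non-inferiority and the first secondary test is about 9% to 10% at the null boundaries, where a conditional sequence would hold it at 5%. This rests on an assumed 145 to 150 livers and on independence; the bound of about 10% does not need independence. If availability is truly 95%, the secondary sequence opens in more than 99% of trials, while the primary is missed in about one trial in five at the planned EAD rates and in 55% to 57% if EAD is 25% in both arms.

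The correction should be made before the analysis. The sentence on survival power is a side issue: it lacks a stated assumption.

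**What to change.** In the synopsis, Protocol 9.3.2 and SAP 5.8 and 12.2, add: *Formal testing of the secondary endpoints (availability, then day-30 survival non-inferiority, then discharge survival non-inferiority) proceeds only if Per Protocol EAD non-inferiority is demonstrated; otherwise secondary results are descriptive.* If the SAP 5.8 display already shows this condition, bring the prose into line with it.

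Leave EAD superiority directly after EAD non-inferiority. State whether the superiority tests and the safety tests are inside or outside the error-controlled claims.

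In Protocol 9.3.2 and SAP 12.2, delete the sentence on survival power or state the survival rates it assumes, separately for day 30 and for discharge.

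Sample size, data collection and test methods do not change. The cost is that no formal secondary claim is possible if the primary fails.

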13. ANALYSIS OF SAFETY

Safety analyses for adverse events will be based on CEC-adjudicated adverse events.

Safety will be analyzed principally by examination of the frequency of liver graft-related serious adverse events (SAEs) up to the 30-day follow-up after transplantation. This endpoint is defined as the number of liver-graft related serious adverse events through 30 days post-liver transplantation per subject, consisting of the following serious adverse events (at most one per type per person):

- Primary non-function (defined as irreversible graft dysfunction requiring emergency liver re-transplantation or death within the first 10 days, in the absence of immunologic or surgical causes)
- Ischemic biliary complications (ischemic biliary strictures and non-anastomotic bile duct leaks)
- Vascular complications (liver graft-related coagulopathy, hepatic artery stenosis, hepatic artery thrombosis, and portal vein thrombosis)
- Liver allograft infections (liver abscess, cholangitis, etc.)

This endpoint will be summarized by treatment group using descriptive statistics. For each treatment group, a 95% confidence interval for the mean based on the t-distribution will be presented. Also, a 95% confidence interval based on the t-distribution will be presented for the difference in means between the two treatments.

For the number of liver graft-related SAEs, the statistical hypotheses are as follows:

$$\begin{aligned} H_{30}: \mu_{OCS} &\geq \mu_{CONTROL} + \delta \text{ and} \\ H_{31}: \mu_{OCS} &< \mu_{CONTROL} + \delta, \end{aligned}$$

where μ_{OCS} and $\mu_{CONTROL}$ are the true mean numbers of liver graft-related SAEs up to the 30-day follow-up after transplantation per subject with the OCS and standard of care treatments, respectively, and δ is the non-inferiority margin, which is here taken to be 1.0. The safety endpoint will be analyzed using a one-sided, two-sample t-test with an alpha level of 0.05. If non-inferiority is demonstrated, a corresponding (two-sided) two-sample t-test of superiority will be performed.

This endpoint will be analyzed based on the As Treated Population.

For each of the four categories of liver graft-related SAEs listed above, the number of subjects with an event and the number of events up to the 30-day follow-up after transplantation will be summarized.

In addition, the numbers and percentages of subjects experiencing at least one treatment-emergent adverse event (TEAE) in the following categories will be tabulated by treatment group: liver graft-related TEAEs, treatment-related (definitely or probably-related) TEAEs, serious TEAEs, and serious liver graft-related TEAEs. The number of treatment-emergent liver graft-related adverse events, treatment-emergent serious adverse events (within 30 days post-

transplant and overall), treatment-emergent serious liver graft-related adverse events (within 30 days post-transplant and overall), treatment-emergent adverse events resulting in study discontinuation, and treatment-emergent serious adverse events with an outcome of death (within 30 days post-transplant and overall) will be tabulated by system organ class and preferred term using MedDRA (Version 13.0 or higher). Liver graft-related TEAEs and liver graft-related serious TEAEs will also be tabulated at the event level by system organ class and preferred term and the relationship of the liver graft-related adverse event to the investigational treatment using counts and percentages. Similar analyses at the event level will be performed by the severity of the adverse event.

The adverse event analyses above will also be presented by subgroup.

An exploratory analysis of the frequency of non-ischemic biliary complications through 30 days post-liver transplantation per subject will be performed. This endpoint will be summarized by treatment group using descriptive statistics. For each treatment group, a 95% confidence interval for the mean based on the t-distribution will be presented. Also, a 95% confidence interval based on the t-distribution will be presented for the difference in means between the two treatments.

